6.6.3.1 Dose adjustments for QTcF prolongation

If QTcF >500 msec or QTcF prolongation >60 msec from baseline is observed at any point during study treatment, and confirmed, the below guidance must be followed:

1. Assess the quality of the ECG recording and the QT value and repeat if needed
2. Interrupt study treatment until confirmed resolution of QTcF to ≤ 480 msec
3. Determine the serum electrolyte levels (in particular hypokalemia, hypomagnesemia). If abnormal, correct abnormalities before resuming study drug treatment.
4. Review concomitant medication associated with QT prolongation, including drugs with a “Known”, “Possible”, or “Conditional risk of Torsades de Pointes” (refer to www.crediblemeds.org), and drugs with the potential to increase the risk of study drug exposure related QT prolongation.
5. Check study drug dosing schedule and treatment compliance.

Increase cardiac monitoring as indicated, until the QTcF returns to ≤ 480 msec.

- After resolution to ≤ 480 msec, consider re-introducing treatment at reduced dose, with increase ECG monitoring for the next treatment
- If QTcF remains ≤ 500 msec after dose reduction, continue planned ECG monitoring during subsequent treatment
- If QTcF recurs > 500 msec after dose reduction, discontinue patient from trial.

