5.2 Exclusion criteria

Participants meeting any of the following criteria are not eligible for inclusion in this study.

1. Known presence of the BCR-ABL1 T315I mutation at any time prior to study entry
2. Known history of AP/BC
3. Previous treatment with a hematopoietic stem-cell transplantation
4. Patient planning to undergo allogeneic hematopoietic stem cell transplantation
5. Cardiac or cardiac repolarization abnormality, including any of the following:
 - History of myocardial infarction (MI), angina pectoris, coronary artery bypass graft (CABG) within 6 months prior to starting study treatment
 - Clinically significant cardiac arrhythmias (e.g., ventricular tachycardia), complete left bundle branch block, high-grade AV block (e.g., bifascicular block, Mobitz type II and third degree AV block, permanent pace maker)
 - QTcF at screening ≥ 450 msec (male patients), ≥ 460 msec (female patients)
 - Long QT syndrome, family history of idiopathic sudden death or congenital long QT syndrome, or any of the following:
 - Risk factors for Torsades de Pointes (TdP) including uncorrected hypokalemia or hypomagnesemia, history of cardiac failure, or history of clinically significant/symptomatic bradycardia
 - Concomitant medication(s) with a “Known risk of Torsades de Pointes” (per www.crediblemeds.org/) that cannot be discontinued or replaced 7 days prior to starting study drug by safe alternative medication.
 - Inability to determine the QTcF interval
6. Severe and/or uncontrolled concurrent medical disease that in the opinion of the investigator could cause unacceptable safety risks or compromise compliance with the protocol (e.g. uncontrolled diabetes, active or uncontrolled infection, pulmonary hypertension)
7. History of acute pancreatitis within 1 year of study entry or past medical history of chronic pancreatitis
8. Patients with known history of Human Immunodeficiency Virus (HIV).

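### The QTcF rule interrupts treatment on a rise of more than 60 msec from baseline, but its resolution, continuation and recurrence steps use absolute values only, so the instructions conflict for baselines below 420 and 440 msec

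*Protocol*

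**What the plan says.** Protocol Section 6.6.3.1 opens with a trigger that has an absolute and a relative part: "If QTcF >500 msec or QTcF prolongation >60 msec from baseline is observed at any point during study treatment, and confirmed". The guidance below it is mandatory. The steps that refer to a QTcF value are:

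- Hold: "Interrupt study treatment until confirmed resolution of QTcF to ≤ 480 msec".
- Re-introduction: "After resolution to ≤ 480 msec, consider re-introducing treatment at reduced dose, with increase ECG monitoring for the next treatment".
- Continuation: "If QTcF remains ≤ 500 msec after dose reduction, continue planned ECG monitoring during subsequent treatment".
- Recurrence: "If QTcF recurs > 500 msec after dose reduction, discontinue patient from trial".

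None of these four mentions change from baseline. The remaining steps cover ECG quality, electrolytes (corrected before dosing resumes), concomitant drugs, and dosing schedule and compliance.

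Three other places bear on the rule:

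- Section 5.2 excludes a screening QTcF of 450 msec or more in men and 460 msec or more in women, with no lower limit. Section 8.4.3 applies the same cut-offs to the mean of three ECGs and sends dose adjustment back to Section 6.6.3.1.
- Section 6.6.3, the parent section, requires discontinuation when a toxicity returns at equal or greater severity after restart on a lower dose. Only cytopenias are excepted. It also requires discontinuation when a non-hematologic toxicity needs an interruption longer than 28 days, and it forbids deviation from mandatory interruptions.
- Table 6-4 has no QTcF row.

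**The concern.** A hold triggered by a change from baseline needs a way to tell when that change has resolved and when it has come back. Here the relative trigger leads into steps that can no longer see it. One ECG can then satisfy two or three instructions that point to different actions.

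This is a mandatory cardiac safety rule. It applies throughout treatment, including after escalation to 200 mg q.d., for which Section 4.2 cites 12 patients with prior exposure. Sites could act differently on the same tracing and each cite the protocol. Under Section 6.6.3, a site that follows the continuation bullet could also be recorded as deviating from a mandatory interruption.

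There is a smaller consequence for the analysis. SAP Section 2.5.3 counts any treatment discontinuation before week 48 as non-response, so the choice between continuing and discontinuing could alter an individual patient's primary outcome.

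**Working it through.** The documents state no figure to reproduce on this point. The check compares the protocol's own thresholds.

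**Inputs.** Relative trigger +60 msec, absolute trigger 500, resolution value 480, and continuation and recurrence boundary 500 (all Section 6.6.3.1). Eligible baseline b is below 450 (men) or 460 (women) (Section 5.2).

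**Formulas.** The relative trigger fires when QTcF > b + 60.

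- Hold required and resolution value already met: b + 60 < QTcF ≤ 480. Such readings exist when b + 60 < 480, that is b < 420. The width is 480 − (b + 60) = 420 − b.
- After dose reduction, interruption trigger and continuation bullet both met: b + 60 < QTcF ≤ 500. Such readings exist when b < 440. The width is 440 − b.
- Rise still present at the resolution value: 480 − b.

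| Baseline b (msec) | Relative trigger | Held but already at or below 480 | Rise at 480 | Interrupt and continue both apply |
|---|---|---|---|---|
| 390 | > 450 | > 450 to 480 (30 wide) | +90 | > 450 to 500 (50 wide) |
| 400 | > 460 | > 460 to 480 (20 wide) | +80 | > 460 to 500 (40 wide) |
| 410 | > 470 | > 470 to 480 (10 wide) | +70 | > 470 to 500 (30 wide) |
| 420 | > 480 | none | +60 | > 480 to 500 (20 wide) |
| 430 | > 490 | none | +50 | > 490 to 500 (10 wide) |
| 440 | > 500 | none | +40 | none |

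**Example for resolution.** Baseline 390, confirmed reading 465. The rise is 465 − 390 = 75, so the hold applies; 465 ≤ 480, so the resolution value is met. A higher reading must fall before re-introduction is considered, but only to 480, where the rise is still 90 and the trigger condition still holds.

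**Example for recurrence.** Baseline 410, reduced dose, confirmed reading 490. The rise is 80, so the trigger calls for interruption. Because 490 ≤ 500, the continuation bullet applies and the recurrence bullet does not. Section 6.6.3 may require discontinuation, depending on whether a repeat rise counts as equal severity, which it does not define for QTcF.

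**How many patients.** The documents do not give the baseline distribution. As an assumption only, take a truncated normal with mean 395 to 425, SD 15 to 25 and cap 450 or 460. Then 37% to 95% of baselines lie below 420, and 79% to more than 99% below 440. If the first excess over +60 is further assumed exponential with mean 5 to 20 msec, 13% to 90% of first relative triggers fall at or below 480.

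**The case against.** The best case for the present text is that a relative alert paired with an absolute resume value may be deliberate, and that other steps supply the protection. Much of this stands. Resolution must be confirmed. The electrolyte, co-medication and compliance checks are mandatory. Re-introduction is only to be considered, at a reduced dose and with more ECGs. Section 8.4.3 averages triplicate ECGs, and Section 9.1.1 requires discontinuation when the investigator believes continuing would harm the patient.

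The continuation bullet can also be read as governing ECG frequency alone, leaving the opening trigger free to fire again. That reading is possible, but the words "after dose reduction, continue planned ECG monitoring during subsequent treatment" assume that treatment goes on, and nothing says which sentence prevails.

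Three stronger readings are tempting, and the documents do not support them:

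- A reader might infer that an interruption for a relative rise ends as soon as it begins. It does not: the confirmation, the work-up and the discretionary reduced-dose restart all still apply.
- A reader might infer that most relative triggers have no working resolution criterion. That needs a baseline distribution the documents lack, and the assumed range above runs from a small minority to a large majority.
- A reader might infer that nothing covers recurrence below 500 msec. The trigger can fire again, and Section 6.6.3 has a general recurrence rule. The fault is competing instructions, not absence of any.

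The argument from comparability is weak. The regimens are not formally compared, and SAP Section 2.7.4.1 tabulates QTcF categories, including rises above 60 msec, from the ECG values whatever dosing action was taken.

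Against the view that the mismatch is deliberate, Table 6-4 does refer resolution to baseline elsewhere, for creatinine and for transaminases elevated at baseline. Section 6.6.3.1 gives no sign that the omission was intended.

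**Conclusion.** The rule is internally inconsistent as written. For eligible baselines below 420 msec, a reading can require a hold while already meeting its resolution value, and re-introduction may be considered while QTcF is still more than 60 msec above baseline. For eligible baselines below 440 msec, a reduced-dose patient can meet the instruction to interrupt and the bullet that presupposes continuation, and possibly a third instruction to discontinue. The resolution step works from 420 msec, and from 440 msec a rise above 60 msec already exceeds 500 msec, so the conflict disappears.

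These breakpoints are exact and rest only on the protocol's thresholds. The share of patients affected is unknown. Because the work-up, the discretionary reduced-dose restart and the added ECGs partly mitigate the risk, this is a correction to make at the next amendment, not a fault of the highest severity. It does not touch the sample size or the primary test.

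**What to change.** Reconcile the steps and bullets of Section 6.6.3.1 with its two-part trigger and with the general recurrence rule in Section 6.6.3. Each trigger should have a stated resolution condition and recurrence condition that match it. If the absolute values are meant to govern both triggers, the text should say so. It should also state which instruction governs a reduced-dose patient at or below 500 msec but more than 60 msec above baseline, and whether the Section 6.6.3 recurrence rule applies to QTcF. The values and the choice of rule belong to the sponsor's medical team; none is proposed here.

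The cost is a few sentences in the next amendment, with its usual approvals, and a notice to sites. No new assessments are needed, since baseline and on-treatment triplicate ECGs are already collected.

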6.6.4 Follow-up for toxicities

Patients whose treatment is permanently discontinued due to a study drug related adverse event or clinically significant laboratory value, must be followed up for 30 days or, until resolution or stabilization of the event. Appropriate clinical specialist should be consulted as deemed necessary. All patients must be followed up for adverse events and serious adverse events for 30 days following the last dose of study treatment.

6.6.4.1 Follow up on potential drug-induced liver injury (DILI) cases

Patients with transaminase increase combined with TBL increase may be indicative of potentially severe Drug-induced liver injury (DILI), and should be considered as clinically important events and assessed appropriately to establish the diagnosis. The required clinical information, as detailed below, should be sought to obtain the medical diagnosis of the most likely cause of the observed laboratory abnormalities.

The threshold for potential DILI may depend on the patient's baseline AST/ALT and TBL value; patients meeting any of the following criteria will require further follow-up as outlined below:

- For patients with normal ALT and AST and TBL value at baseline: AST or ALT > 3.0 x ULN combined with TBL > 2.0 x ULN
- For participant with elevated AST or ALT or TBL value at baseline: [AST or ALT > 3 x baseline] OR ALT or AST > 8.0 x ULN], whichever occurs first, combined with [TBL > 2.0 x baseline AND > 2.0 x ULN]

As DILI is essentially a diagnosis of exclusion, other causes of abnormal liver tests should be considered, and their role clarified before DILI is assumed as the cause of liver injury.

A detailed history, including relevant information such as review of ethanol consumption, concomitant medications, herbal remedies, supplement consumption, history of any preexisting liver conditions or risk factors, should be collected.

Laboratory tests should include ALT, AST, TBL, direct and indirect bilirubin, GGT, prothrombin time (PT)/INR, alkaline phosphatase, albumin, and creatine kinase. If available, testing of Glutamate Dehydrogenase (GLDH) is additionally recommended.

Evaluate status of underlying malignancy for an extra-medullary hepatic involvement.

Perform relevant examinations (Ultrasound or MRI, Endoscopic retrograde cholangiopancreatography (ERCP)) as appropriate, to rule out an extrahepatic cause of cholestasis. Cholestasis (is defined as an Alkaline Phosphatase (ALP) elevation > 2.0 x ULN with R value < 2 in patients without bone metastasis, or elevation of the liver-specific ALP isoenzyme in patients with bone metastasis).

Note: The R value is calculated by dividing the ALT by the ALP, using multiples of the ULN for both values. It denotes whether the relative pattern of ALT and/or ALP elevation is due to cholestatic ($R \leq 2$), hepatocellular ($R \geq 5$), or mixed ($R > 2$ and < 5) liver injury. In clinical situations where it is suspected that ALP elevations are from an extrahepatic source, the GGT can be used if available. GGT may be less specific than ALP as a marker of cholestatic injury, since GGT can also be elevated by enzyme induction or by ethanol consumption. It is more sensitive than ALP for detecting bile duct injury. Table 6-5 provides guidance on specific

clinical and diagnostic assessments which can be performed to rule out possible alternative causes of observed Liver function test (LFT) abnormalities.

Table 6-5 Clinical and diagnostic assessments to rule out possible alternative causes of observed LFT abnormalities

Disease	Assessment
Hepatitis A, B, C, E	IgM anti-HAV; HBsAg, IgM & IgG anti-HBc, HBV DNA; anti-HCV, HCV Ribonucleic acid (RNA), IgM & IgG anti-HEV, HEV RNA
CMV, HSV, EBV infection	IgM & IgG anti-CMV, IgM & IgG anti-HSV; IgM & IgG anti-EBV
Autoimmune hepatitis	Antinuclear Antibodies (ANA) & Anti-Smooth Muscle Antibody (ASMA) titers, total IgM, IgG, IgE, IgA
Alcoholic hepatitis	Ethanol history, GGT, MCV, CD-transferrin
Nonalcoholic steatohepatitis	Ultrasound or MRI
Hypoxic/ ischemic hepatopathy	Medical history: acute or chronic congestive, heart failure, hypotension, hypoxia, hepatic venous occlusion. Ultrasound or MRI
Biliary tract disease	Ultrasound or MRI, ERCP as appropriate.
Wilson disease (if <40 yrs old)	Caeruloplasmin
Hemochromatosis	Ferritin, transferrin
Alpha-1-antitrypsin deficiency	Alpha-1-antitrypsin

Other causes should also be considered based upon patients’ medical history (hyperthyroidism / thyrotoxic hepatitis – T3, T4, TSH; cardiovascular disease / ischemic hepatitis – ECG, prior hypotensive episodes; Type 1 diabetes / glycogenic hepatitis).

Obtain PK sample to determine exposure to study treatment and metabolites.

Following appropriate causality assessments, as outlined above, the causality of the treatment is estimated as “probable” i.e. >50% likely, if it appears greater than all other possible causes of liver injury combined. The term “treatment-induced” indicates probably caused by the treatment, not by something else, and only such a case can be considered a DILI case and should be reported as an SAE.

All cases confirmed on repeat testing meeting the laboratory criteria defined above, with no other alternative cause for LFT abnormalities identified, should be considered as “medically significant”, and thus, meet the definition of SAE and should be reported as SAE using the term “potential treatment -induced liver injury”. All events should be followed up with the outcome clearly documented.

6.6.4.2 Additional treatment guidance

6.6.5 Treatment compliance

The investigator must promote compliance by instructing the participant to take the study treatment exactly as prescribed and by stating that compliance is necessary for the participant’s safety and the validity of the study. The participant must also be instructed to contact the investigator if he/she is unable for any reason to take the study treatment as prescribed.

Total daily dose of study treatment administered with start and end date and dosing will be collected on the appropriate eCRF page. Name, start and end dates of any Concomitant

Medications and Surgical and Medical procedures will be collected on the Prior and Concomitant medications and Surgical and Medical procedures eCRFs respectively.

Compliance will be assessed by the investigator and/or study personnel at each patient visit and information provided by the patient and/or caregiver will be captured in the Drug Accountability Form. This information must be captured in the source document at each dispensing patient visit.

6.6.6 Emergency breaking of assigned treatment code

Not applicable.

7 Informed consent procedure

Eligible participants may only be included in the study after providing (witnessed, where required by law or regulation), IRB/IEC-approved informed consent.

If applicable, in cases where the participant's representative(s) gives consent (if allowed according to local requirements), the participant must be informed about the study to the extent possible given his/her understanding. If the participant is capable of doing so, he/she must indicate agreement by personally signing and dating the written informed consent document.

Informed consent must be obtained before conducting any study-specific procedures (e.g. all of the procedures described in the protocol). The process of obtaining informed consent must be documented in the participant source documents.

Novartis will provide to investigators in a separate document a proposed informed consent form that complies with the ICH GCP guidelines and regulatory requirements and is considered appropriate for this study. Any changes to the proposed consent form suggested by the investigator must be agreed by Novartis before submission to the IRB/IEC.

As per (Section 4.6), if the covid-19 pandemic challenges the ability to obtain a standard written informed consent due to limits that prevent an on-site visit, the Investigator may conduct the informed consent discussion remotely (e.g. telephone, videoconference) if allowable by a local Health Authority.

Guidance issued by local regulatory bodies on this aspect prevail and must be implemented and appropriately documented (e.g. the presence of an impartial witness, sign/dating separate ICFs by trial participant and person obtaining informed consent, etc.).

Information about common side effects already known about the investigational drug can be found in the Asciminib Investigator's Brochure (IB). This information will be included in the participant informed consent and should be discussed with the participant during the study as needed. Any new information regarding the safety profile of the investigational drug that is identified between IB updates will be communicated as appropriate, for example, via an investigator notification or an aggregate safety finding. New information might require an update to the informed consent and then must be discussed with the participant.

The following informed consents are included in this study:

- Main study consent, which also includes:

- A subsection that requires a separate signature for tests that are optional. This section refers to optional participation in the CCI research collaboration that will be conducted in Europe and Russia. Refer to (Section 8.1).
- A subsection that requires a separate signature for the ‘Optional Consent for Additional Research’ to allow future research on data/samples collected during this study.
- A subsection that requires a separate signature for the ‘Optional consent for activities that may be done outside of the study site’ to allow some study activities to be done outside of the study site (for example, at participants home or at another suitable offsite location) due to measures implemented as a result of the COVID-19 pandemic, such as travel restrictions or closures of local hospitals and patient treatment facilities.
- As applicable, Pregnancy Outcomes Reporting Consent for female participants

Women of child bearing potential must be informed that taking the study treatment may involve unknown risks to the fetus if pregnancy were to occur during the study and agree that in order to participate in the study they must adhere to the contraception requirements for the duration of the study. If there is any question that the patient will not reliably comply, they should not be entered in the study.

The study includes an optional consent for additional research component which requires a separate signature if the participant agrees to participate as mentioned above. It is required as part of this protocol that the Investigator presents this option to the participants, as permitted by local governing regulations. The process for obtaining consent should be exactly the same as described above for the main informed consent.

Declining to participate in these optional studies will in no way affect the participant’s ability to participate in the main research study.

The study also includes an optional consent for home-nursing visits “activities that may be done outside of the study site” which requires a separate signature if the participant agrees to participate as mentioned above. If certain clinical trial procedures need to be done off site due to temporary inability to perform on site visit due to COVID-19, participant may be proposed this option, if permitted by local laws and feasible.

The process for obtaining consent should be exactly the same as described above for the main informed consent.

A copy of the approved version of all consent forms must be provided to Novartis after IRB/IEC approval.

8 Visit schedule and assessments

The Assessment Schedule (Table 8-1) lists all the assessments and indicates with an “X”, the visits when they are performed. All data obtained from these assessments must be documented in the participant’s source documentation. Patients can be consented for study participation prior to study day -28.

Participants should be seen for all visits/assessments as outlined in the assessment schedule (Table 8-1) or as close to the designated day/time as possible. Missed or rescheduled visits should not lead to automatic discontinuation.

Participants who discontinue from study treatment are to return for the end of treatment visit as soon as possible, and attend the follow-up visits as indicated in the Assessment Schedule.

Participants who discontinue from study or withdraw their consent/oppose the use of their data/biological samples should be scheduled for a final evaluation visit if they agree, as soon as possible, at which time all of the assessments listed for the final visit will be performed. At this final visit, all dispensed investigational product should be reconciled, and the adverse event and concomitant medications not previously reported must be recorded on the CRF.

As per Section 4.6, if the COVID-19 pandemic limits or prevents on-site study visits, alternative methods of providing continuing care may be implemented by the investigator as the situation dictates. If allowed by local Health Authority and depending on operational capabilities, phone calls, virtual contacts (e.g. tele consult) or visits by site staff/ home nursing staff to the participant's home, can replace on-site study visits, for the duration of the disruption due to the pandemic until it is safe for the participant to visit the site again. Screening visit and week 1 day 1 visits must be done on site.

The "X" in the table denotes the assessments to be recorded in the clinical database or received electronically from a vendor. The "S" in the table denotes the assessments that are only in the participant's source documentation and do not need to be recorded in the clinical database.

No eCRF will be used as a source document.

(S) is defined as "Source"

(D) is defined as "Data Based"

Study visits from Week 1 Day 1 to Week 2 Day 1 should be completed on the designated date [with an allowed "visit window" of +/- 1 day for Week 1 Day 1 and Week 2 Day 1]

Study visits from Week 4 to Week 12 should be completed every 4 weeks on the designated date [with an allowed "visit window" of +/- 2 day]

Study visits after Week 12 (from Week 24) to EOT should be completed every 12 weeks on the designated date [with an allowed "visit window" of +/- 7 days].

Safety follow-up should be completed 30 days from the last dose of study treatment [with an allowed "visit window" of +/- 7 days].

Visit at weeks 62, 74, 86, 98, 110 or 122 that is two weeks post dose escalation should be completed once after dose escalation on the designated date [with an allowed "visit window" of +/- 1 day].

A delayed visit will have no impact on the next planned visit. The next visit should be completed as scheduled in order to avoid accumulation of additional weeks.

Visit name	Category	Protocol Section	Screening Phase	Treatment Phase										EOT (week 144) /Early Discontinuation	Safety follow-up ¹³		
				Screening/ Baseline	Week 1 Day 1	Week 2 Day 1	Week 4	Week 8	Week 12	Week 24	Week 36	Week 48	Every 12 weeks up to week 132 (w60, w72, w84, w96, w108, w120, w132)			Week 62/74/86/98/ 110/122 for patient dose escalating	
Days (+/- X days)			Day -28 to -1	1 (+/- 1 day)	8 (+/- 1 day)	29 (+/- 2 days)	57 (+/- 2 days)	85 (+/- 2 days)	169 (+/- 7 days)	253 (+/- 7 days)	337 (+/- 7 days)	(+/- 7 days)	(+/- 1 day)	(+/- 7 days)	(+/- 7 days)		
Prior/concomitant medications	D	8.2	X	Continuous													
Physical Examinations	S	8.4	X	X		X	X	X	X	X	X	X		X			
Extra medullary Involvement	D		X														
ECOG Performance status	D	8.4.1	X	X		X	X	X	X	X	X	X		X			
Height	D	8.4	X														
Weight	D	8.4	X	X				X	X	X	X	X		X			
Vital signs ¹	D	8.4	X	X	X	X	X	X	X	X	X	X		X			
Laboratory assessments		8.4.2															
Hematology	D	8.4.2	X	X	X	X	X	X	X	X	X	X	X	X			
Chemistry ²	D	8.4.2	X	X	X	X	X	X	X	X	X	X	X	X			
Coagulation	D	8.4.2	X	As clinically indicated													

1. Blood Pressure reading to be taken in the supine position for all visits.
2. Hemoglobin A1c to be collected at screening only.
3. A monthly urine pregnancy test must be performed by all women of child-bearing potential between the three monthly visits at the investigational site. Urine pregnancy tests may be performed at the investigational site or at home. Test results performed at home should be recorded in a patient diary and brought to each scheduled visit for the site to review. If a test result indicates a pregnancy, the patient must contact the investigator immediately.
4. Only required for Early Discontinuation due to lack of response / loss of response.
5. Same tube will be used for RQ PCR CCI [REDACTED]
6. For patients who are not in MMR at week 48 and for patients losing the response after week 48 assessments up to week 108 and who may benefit from a dose escalation, CCI [REDACTED].
7. Samples to be collected before first dose and 2 to 4 hours post dose.
8. After week 48, the ECG assessments will be done at week 60, week 84, week 108 and week 132 for patients on standard dose (80mg q.d. and 40mg b.i.d.).
9. For patients with dose escalation ECG assessment to be conducted: at dose escalation visit (pre-dose and two hours post-dose), two weeks post-dose escalation, 3 months post-dose escalation, 6 months post-dose escalation, 6 monthly thereafter. Please refer to [Section 8.4.3](#) for more information.
10. Personal and family history of the following conditions: Coronary artery disease, Hyperlipidaemia, Type 1 diabetes mellitus, Type 2 diabetes mellitus, Hypertension, medication taken for hypertension, Myocardial infarction or Cerebrovascular accident will be collected at screening. History of smoking, physical activity and diet will be collected at screening and end of treatment.
11. Week 24 echocardiogram can be performed within a window of +/- 4 weeks of the visit
12. After week 48, PRO assessment will be done every 24 weeks up to week 120 (i.e. these assessments will be completed at week 72, week 96 and week 120).
13. Safety follow-up may be done on site or via phone call with patient. The safety follow-up to be completed 30 days from the last dose of study treatment.

